An EoT Visit should occur within 3 days of the last dose of study drug (or within 3 days of decision to permanently stop drug treatment, if this decision directly follows a period when drug has been on hold) and before the start of any subsequent anticancer therapy. A Safety Follow-up Visit should occur 30 days (± 3 days) after the EoT Visit and if possible before the start of any subsequent anticancer therapy. After the EoT Visit, patients who have not progressed/relapsed will enter the Disease Follow-up period, during which response assessments will be performed for up to 5 years after discontinuation of study drug (irrespective of initiation of HSCT or other subsequent anticancer therapy) or until disease progression/relapse, death, or the occurrence of the expected number of OS events to support the final OS analysis, whichever occurs first. It is estimated that a final analysis of OS will occur approximately 70 months following the enrollment of the first patient.

Patients who progress/relapse will enter Survival Follow-up and will be followed to document the start of subsequent anticancer therapy, the date of disease progression/relapse, the date of transformation to AML, and OS status until the expected number of OS events to support the final OS analysis is observed.

An IDMC will be established and will review the data at the 2 planned interim futility analyses and the safety interims, as specified in the IDMC Charter.

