8.3.1 Time Period and Frequency for Collecting AE and SAE Information

AEs and SAEs will be captured from the time of the first study drug administration through the Safety Follow-up Visit.

All SAEs will be recorded and reported to the sponsor or designee immediately without undue delay and under no circumstance should this exceed 24 hours, as indicated in Appendix 3. The

investigator will submit any updated SAE data to the sponsor immediately without undue delay and within 24 hours of it being available.

Investigators are not obligated to actively seek information on AEs or SAEs after conclusion of the study participation. However, if the investigator learns of any SAE, including a death, at any time after a patient has been discharged from the study, and he/she considers the event to be reasonably related to the study drug or study participation, the investigator must promptly notify the sponsor.

Contact information for the Pharmacovigilance group is provided in Appendix 3.

Germany only: AEs and SAEs will be captured from the time of the first study drug administration through the Safety Follow-up Visit.

All SAEs will be recorded and reported to the sponsor or designee immediately without undue delay, as indicated in Appendix 3. The investigator will submit any updated SAE data to the sponsor immediately without undue delay.

Investigators are not obligated to actively seek information on AEs or SAEs after conclusion of the study participation. However, if the investigator learns of any SAE, including a death, at any time after a patient has been discharged from the study, and he/she considers the event to be reasonably related to the study drug or study participation, the investigator must promptly notify the sponsor.

Contact information for the Pharmacovigilance group is provided in Appendix 3.

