10.3.4 Reporting of SAEs

SAE Reporting to Pharmacovigilance Group

- An SAE Report form will be completed and submitted to the sponsor's designee via email at PPD or Fax #: PPD immediately without undue delay and within 24 hours of the investigator's first knowledge of the event, even if the experience does not appear to be related to study drug.

 Germany only: An SAE Report form will be completed and submitted to the sponsor's designee via email at PPD or Fax #: PPD immediately without undue delay from the investigator's first knowledge of the event, even if the experience does not appear to be related to study drug.
- The initial SAE Report form must be as complete as possible, including details of the current illness and SAE and an assessment of the relationship between the event and the study drug. Additional information relating to a previously reported SAE must also be reported immediately without undue delay and within 24 hours of the investigator's first knowledge of information. The investigator may also be asked by the sponsor to provide clarification or additional information.
 - *Germany only:* The initial SAE Report form must be as complete as possible, including details of the current illness and SAE and an assessment of the relationship between the event and the study drug. Additional information relating to a previously reported SAE must also be reported immediately without undue delay from the investigator's first knowledge of information. The investigator may also be asked by the sponsor to provide clarification or additional information.
- If the investigator becomes aware of an SAE considered related to study drug by the investigator occurring more than 30 days after the last dose of study drug, the SAE must be reported as described above.

10.3.5 Reporting of Serious Adverse Events to Regulatory Authorities, Ethics Committees, and Institutional Review Board

The sponsor will determine the expectedness for each reported SAE based on the appropriate reference safety information per local requirements. The sponsor or designee shall notify regulatory authorities of serious, unexpected, and related AEs or other AEs per local requirements. The sponsor or designee shall notify the investigator of serious, related, and unexpected AE(s) per local country requirements.

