7.1.3.3 Imputation of Partial or Missing AE Dates for Analysis

Rules for imputing partial or missing AE dates for analysis are provided in Table 10.

Adverse Events	Partial/missing AE dates recorded in the CRF will
	be imputed using the following conventions:

Missing start day	The first of the month will be used unless it is before
	the start date of study treatment; in this case, the study
	treatment start date will be used and hence the event is
	considered treatment emergent.
Missing start day and month	No imputation.
Missing end day	Last day of the month will be used.
Missing end day and month	No imputation.
Completely missing start/end	No imputation.
day	

Abbreviations: AE = adverse event; CRF = case report form

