7.1.3.4 Imputation of Partial or Missing Medical History/Concomitant Medication Dates for Analysis

Rules for imputing partial or missing medical history or concomitant dates for analysis are provided in Table 11.

Table 11Date Imputation Rules for Medical History/Prior and Concomitant
Medications/Prior Cancer Therapy

Medical History/Prior and Concomitant Medications/Prior Cancer Therapy	Partial/Missing Medical History/Prior and Concomitant Medication/Prior Cancer Therapy Dates Recorded in the CRF Will Be Imputed Using the Following Conventions:
Missing start day	'01' will be used for the day.
Missing start day and month	'01' will be used for the day and 'Jan' will be used for the month.
Missing end day	 '28/29/30/31' will be used for the day (dependent on the month and year) and the earlier of last day of the month and the end of study date will be used as the imputed value except in the following two cases: 1) For prior cancer therapy 2) If it is not ongoing and the start date is prior to the study treatment start date For these two cases, the end date will be imputed as (study treatment start date -1).

Version 4.0

Missing end day and month

'31' will be used for the day and 'Dec' will be used for
the month, and the earlier of 31 Dec of the given year
and the end of study date will be used as the imputed

	and the end of study date will be used as the imputed
	value except in the following two cases:
	1) For prior cancer therapy
	2) If it is not ongoing and the start date is prior to the
	study treatment start date
	For these two cases, the end date will be imputed as
	(study treatment start date -1).
Completely missing start/end	No imputation.
day	

Imputation of Partial or Missing New Anticancer Therapy Dates for 7.1.3.5 Efficacy Evaluation

Start dates for follow-up anticancer therapy will be temporarily imputed in order to define event and censoring rules for EFS, response rate, time to event, duration of response, or time to response (e.g., start date for new anticancer therapy). The imputed dates will be stored in the anticancer therapy-derived dataset.

- If missing start day, month, and year, then no imputation.
- If missing start day and month, then no imputation.
- If missing start day only, then do the following: •
 - If partial date falls in the same month as the last dose of study treatment, then assign to earlier of (date of last dose of study treatment + 1, last day of month).

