7.6.1 Adverse Events

Treatment-emergent adverse events (TEAEs) are defined as those AEs with onset after the first dose of study drug or existing events that worsened after the first dose during the study up until the last dose of study drug + 30 days. TEAEs will be summarized by treatment group. Selected TEAEs will also be summarized. The selected TEAEs include rash, pain, hypertriglyceridemia, venous thrombosis, anemia/RBC count decreased, thrombocytopenia/platelet count decreased, neutropenia/neutrophil count decreased, and leukopenia/white blood cell (WBC) count decreased. A detailed search strategy for the selected TEAE groups is provided in Appendix 1.

AEs with missing start and/or stop dates will be considered TEAEs. Imputation rules for partial and missing dates are described in Table 10.

Verbatim terms on CRFs will be mapped to PTs and SOCs using MedDRA, version 23.1 or higher. AEs will be graded using the National Cancer Institute (NCI) CTCAE version 5. If an AE grade is missing, the previous worst grade under the same PT will be assigned if it is available, otherwise a grade of 4 will be assigned for classification purposes in the TLFs.

The CTCAE Grade will be summarized by grouping Grade 1 and Grade 2 together, then Grade 3 and Grade 4 together, as well as Any Grade for all relevant TEAE tables.

Summaries of the following types will be presented by treatment group:

• Overall summary of the number of TEAEs, TEAEs by relationship to tamibarotene/placebo and azacitidine, TEAEs by CTCAE grade, serious AEs (SAEs), SAEs related to tamibarotene/placebo and azacitidine, selected TEAEs, TEAEs requiring concomitant medications, TEAEs leading to dose interruption of tamibarotene/placebo and azacitidine, TEAEs leading to dose reduction of tamibarotene/placebo and azacitidine, TEAEs leading to discontinuation of
tamibarotene/placebo and azacitidine, TEAEs leading to death (overall summary will also be analyzed based on mITT who received at least 1 study dose)

- TEAEs by SOC and PT
- TEAEs by PT
- TEAEs occurring in $\geq 10\%$ of participants in any treatment group by PT
- TEAEs related to tamibarotene/placebo by PT
- TEAEs related to azacitidine by PT
- TEAEs by CTCAE grade, SOC and PT
- TEAEs by CTCAE grade and PT
- TEAEs related to tamibarotene/placebo by CTCAE grade and PT
- TEAEs related to azacitidine by CTCAE grade and PT
- SAEs by SOC and PT
- SAEs by PT
- SAEs occurring in \geq 5% of participants in any treatment group by PT

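### SAP 7.6.1 lets a missing stop date alone make an AE treatment-emergent, even when its known onset falls after last dose + 30 days

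*SAP*

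**What the plan says.** SAP 7.6.1 gives the definition in two limbs. The first is new onset: "Treatment-emergent adverse events (TEAEs) are defined as those AEs with onset after the first dose of study drug". The second is worsening: "existing events that worsened after the first dose during the study up until the last dose of study drug + 30 days". The same section then gives a default for incomplete dates: "AEs with missing start and/or stop dates will be considered TEAEs".

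Table 10 (SAP 7.1.3.3) makes no imputation in the row headed "Completely missing start/end", so an AE with no recorded end date keeps a blank one. No AE rule treats an ongoing event differently from one whose stop date is unknown. For medications and prior therapy the SAP does draw that line: one condition in Table 11 reads "If it is not ongoing and the start date is prior to the study treatment start date".

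On collection, Protocol 8.3.1 says: "AEs and SAEs will be captured from the time of the first study drug administration through the Safety Follow-up Visit". Protocol 4.1 times that visit from End of Treatment (EoT), at 30 ± 3 days, and not from last dose. EoT itself falls within 3 days of last dose or "within 3 days of decision to permanently stop drug treatment, if this decision directly follows a period when drug has been on hold". Protocol 7.1 and Schedule of Activities footnotes (c) and (d) allow EoT and Safety Follow-up to be combined when EoT is at least 30 days after last dose. Protocol 10.3.4 adds that, for a related SAE "occurring more than 30 days after the last dose of study drug, the SAE must be reported".

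**The concern.** The definition depends on when an event began or worsened. The default depends on whether a date field is filled in. The *and/or* makes a missing stop date sufficient by itself, even when the start date is complete and lies outside the window. An unresolved AE would ordinarily have no stop date, so for a late onset the classification would follow resolution and not timing.

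Two things are at stake. Two late events with the same onset could be handled differently in the AE tables of SAP 7.6.1, nearly all of which are built on TEAE status. One event could also change status between data cuts: Protocol 8.3.3 has SAEs followed until they resolve or stabilize, so a late SAE open at the CR analysis could count as a TEAE there and drop out of the final OS report once its stop date is entered. The SAP treats day 30 as a real boundary elsewhere in the same section, where deaths are split at 30 days after last dose.

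**Working it through.** The plan states no figure to reproduce. The check has two parts: whether AEs with onset after last dose + 30 days can be in the data, and what the rule does with them. Day 0 is the last dose of study drug.

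**1. How far routine AE capture can run**

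End of capture = day of EoT + interval from EoT to Safety Follow-up. The interval is 30 ± 3, so 27 to 33 days (Protocol 4.1). Excess = end of capture − 30, or 0 if negative.

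- *No hold.* EoT is on day 0 to 3. Earliest end: 0 + 27 = day 27, excess 0. Latest end: 3 + 33 = day 36, excess 6. At the nominal 30-day interval the end is day 30 to 33, excess 0 to 3.
- *28-day hold of both drugs, then a decision to stop.* The 28 days are illustrative, taken from the interruption length in Protocol 7.1. The decision falls on day 28 and EoT on day 28 to 31.
  - Visits combined, which is allowed when EoT is on day 30 or later: capture ends on day 30 or 31, excess 0 to 1.
  - Visits separate: the latest end is 31 + 33 = day 64, excess 34.
- *Related SAEs.* Protocol 10.3.4 requires reporting beyond 30 days after last dose, and that section sets no upper limit.

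So onsets after day 30 can be recorded. The 6 and 34 days are maxima that need every visit window used in full.

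**2. What the rule does with such an event**

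Literal rule: a missing start or stop date gives a TEAE; otherwise onset must lie between first dose and day 30. Comparison rule: status follows onset, and the default applies only when the start date is missing.

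| Onset day | Stop day | Literal SAP rule | Onset-based rule |
|---|---|---|---|
| 20 | blank | TEAE | TEAE |
| 20 | 40 | TEAE | TEAE |
| 30 | blank | TEAE | TEAE |
| 31 | blank | TEAE | not a TEAE |
| 31 | 35 | not a TEAE | not a TEAE |
| 34 | blank | TEAE | not a TEAE |
| 34 | 40 | not a TEAE | not a TEAE |

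Up to day 30 the stop date makes no difference. From day 31 the literal rule gives opposite answers for the same onset. Events before first dose are largely unaffected, because Protocol 8 sends them to medical history.

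**The case against.** The strongest reply is that the flip depends on how two phrases are read.

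- *Missing* may have been meant to exclude events recorded as ongoing, as Table 11 suggests for medications. The problem would then shrink to resolved late events with an unknown stop date.
- The 30-day limit may attach only to existing events that worsened. Every late onset would then be a TEAE and nothing would flip.

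Both readings are possible, but the SAP states neither for AEs. The usual reading applies the limit to both limbs. If either alternative was intended the text should say so, because two programmers could produce different tables.

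The reply also limits the size of the problem, and this stands. The window is narrow with no hold. With a long hold, combining the visits nearly closes it. Study drug means tamibarotene/placebo and azacitidine (Protocol 6), and Protocol 6.5.1 lets one continue while the other is held, so the hold case needs both stopped. The stop-date trigger can only add events to the TEAE tables, and all AEs are listed.

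A reader might infer that AEs leading to discontinuation are misclassified, or that the arm with more holds is affected more. The documents support neither. With no hold, dosing has already ended before day 31. After a 28-day hold the stop decision comes on day 28, so an onset on day 31 or later cannot have caused it; only a longer hold of both drugs could produce such a case. No hold rates by arm are given.

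**Conclusion.** The point holds as a minor one. The missing-date sentence conflicts with the SAP's own definition for AEs with a known onset after last dose + 30 days, and no other rule in the SAP removes the conflict.

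It rests on two assumptions: that ongoing AEs have a blank stop date and are not exempted, and that the 30-day limit covers new onsets as well as worsening. The number of affected events cannot be derived from the documents and is probably small. It would be wrong to read 6 to 34 days as a typical exposure per participant, because these are the maxima of two different scenarios and each can be zero or close to it. No efficacy result is affected.

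**What to change.** Replace the sentence in SAP 7.6.1 with:

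> TEAE status is determined by the date of onset or worsening. An AE whose start date is missing or partial is considered a TEAE unless the available dates show that it ended before first dose, that it began before first dose and did not worsen between first dose and last dose + 30 days, or that it began more than 30 days after last dose. A missing stop date, including for an ongoing AE, does not by itself make an AE treatment-emergent.

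This keeps the cautious default where onset cannot be placed, and it keeps pre-existing events that worsened inside the window. An onset on day 34 is then outside the TEAE tables whether or not it has resolved, and an onset on day 20 is inside them in both cases. The new-onset limb of the definition should also say explicitly that the 30-day limit applies to it. The cost is a short edit to one SAP section and one programming condition; no new data are needed.

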10.3.3 Recording and Follow-up of AE and/or SAE

AE and SAE Recording

- When an AE/SAE occurs, it is the responsibility of the investigator to review all documentation (e.g., hospital progress notes, laboratory reports, and diagnostics reports) related to the event.
- The investigator will then record all relevant AE/SAE information.
- It is **not** acceptable for the investigator to send photocopies of the patient's medical records to the Pharmacovigilance group in lieu of completion of the SAE required form.
- The investigator will attempt to establish a diagnosis of the event based on signs, symptoms, and/or other clinical information. Whenever possible, the diagnosis (not the individual signs/symptoms) will be documented as the AE/SAE.

Assessment of Severity

The investigator will make an assessment of severity (Grades 1 through 5) for each AE and SAE reported during the study using National Cancer Institute CTCAE, version 5.

An event is defined as 'serious' when it meets at least 1 of the predefined outcomes as described in the definition of an SAE, NOT when it is rated as severe.

Assessment of Causality

- The investigator is obligated to assess the relationship between study drug and each occurrence of each AE/SAE.
- Related assessment is reported when a "reasonable possibility" of a relationship conveys that there are facts, evidence, and/or arguments to suggest a causal relationship, rather than a relationship cannot be ruled out.
- The investigator will use clinical judgment to determine the relationship.
- Alternative causes, such as underlying disease(s), concomitant therapy, and other risk factors, as well as the temporal relationship of the event to study drug administration, will be considered and investigated.
- The investigator will also consult the IB and/or Product Information, for marketed products, in his/her assessment.
- There may be situations in which an SAE has occurred, and the investigator has minimal information to include in the initial report to the Pharmacovigilance group. However, it is very important that the investigator always makes an assessment of causality for every event before the initial transmission of the SAE data to the Pharmacovigilance group. It is helpful if the investigator includes the rationale for the assessment as being causally related, or not causally related, in the transmission of the SAE data.

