- SAEs related to tamibarotene/placebo by PT
- SAEs related to azacitidine by PT
- Selected TEAEs by PT
- Selected TEAEs related to tamibarotene/placebo by PT
- Selected TEAEs related to azacitidine by PT
- Selected TEAEs by PT and CTCAE grade
- Selected TEAEs related to tamibarotene/placebo by PT and CTCAE grade
- Selected TEAEs related to azacitidine by PT and CTCAE grade
- TEAEs requiring concomitant medications by PT
- TEAEs related to tamibarotene/placebo requiring concomitant medications by PT
- TEAEs related to azacitidine requiring concomitant medications by PT
- TEAEs leading to dose interruption of tamibarotene/placebo by PT
- TEAEs leading to dose interruption of azacitidine by PT
- TEAEs leading to dose reduction of tamibarotene/placebo by PT
- TEAEs leading to dose reduction of azacitidine by PT
- TEAEs leading to discontinuation of tamibarotene/placebo by PT
- TEAEs leading to discontinuation of azacitidine by PT

The overall summary of TEAEs will also be created for Safety Analysis Set 2, while all other safety outputs will be created only for Safety Analysis Set 1.

All deaths will be summarized based on the number and percentage of participants. This summary will classify participants by time of death relative to the last dose of treatment (>30 days or \leq 30 days) and analyze the primary cause of death. Off-treatment deaths (deaths occurring >30 days after the last dose of treatment) will only be summarized at the prespecified IA and the final OS analysis or based on a regulatory request.

Summaries by SOC and PT will be ordered by descending incidence of SOC and PT within each SOC based on the tamibarotene plus azacitidine group. Summaries by PT will be ordered by descending incidence of PT for the tamibarotene plus azacitidine group. At each level of summarization (e.g., any AE, SOC, and PT), participants experiencing more than 1 TEAE will be counted only once. In the summary of TEAEs by severity grade, participants will be counted once at the highest severity reported at each level of summarization; in the summary of TEAEs by relationship, participants will be counted once at the closest relationship to the indicated study drug (tamibarotene/placebo or azacitidine).

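### TEAE tables by grade have no Grade 5 or Grade ≥3 column, so a participant with a fatal TEAE leaves the Grade 3–4 count and the severe-grade comparison between arms is distorted

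*SAP*

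**What the plan says.** **Scale collected.** Protocol 10.3.3, using CTCAE version 5: "The investigator will make an assessment of severity (Grades 1 through 5) for each AE and SAE reported during the study". SAP 7.6.1 uses the same version.

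**Display.** SAP 7.6.1: "The CTCAE Grade will be summarized by grouping Grade 1 and Grade 2 together, then Grade 3 and Grade 4 together". A further column combines every grade, and the rule is meant for each TEAE table that shows severity. The section names no Grade 5, Grade 3–5 or Grade ≥3 category for adverse events.

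**Counting.** For the TEAE summaries by severity, SAP 7.6.1 states that "participants will be counted once at the highest severity reported at each level of summarization". The levels are any AE, system organ class (SOC) and preferred term (PT).

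**Missing grades.** The earlier worst grade under the same PT is used if there is one; "otherwise a grade of 4 will be assigned for classification purposes in the TLFs".

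**Fatal events elsewhere.** The overall TEAE summary has a line for TEAEs that led to death. There is also a deaths table: "All deaths will be summarized based on the number and percentage of participants", split at 30 days after the last dose and by primary cause. Adverse events leading to death, and deaths, are listed separately.

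**The concern.** Grades 1 to 5 are recorded, but the severity columns cover only Grades 1 to 4. With worst-grade counting the columns exclude one another, so a participant at Grade 5 fits none of them except Any Grade.

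Someone comparing severe toxicity between arms in the by-grade tables has only the Grade 3–4 column to use. A fatal TEAE lowers that column instead of leaving it unchanged or raising it. If fatal TEAEs are more frequent in one arm, that arm's severe-grade figure is reduced by more, and the comparison moves in its favour.

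The rule covers all the planned by-grade tables in SAP 7.6.1: all TEAEs, TEAEs related to each study drug, and the selected TEAEs. SAP 7.6.2 does explain leaving out Grade 5, but only for laboratory grading, because laboratory data cannot show death. That reason does not carry over to events graded by the investigator.

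**Working it through.** The plan gives no figure to reproduce. The check sets the rules against each other and then shows the arithmetic that follows.

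**Step 1. Where a fatal TEAE lands.**

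| Worst grade in the row | Grade 1–2 | Grade 3–4 | Any Grade |
|---|---|---|---|
| 1 or 2 | counted | – | counted |
| 3 or 4 | – | counted | counted |
| 5 | – | – | counted |

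- In the any-TEAE row, one fatal event removes the participant from Grade 3–4 whatever other Grade 3–4 events they had.
- In a SOC row, the loss is confined to the SOC of the fatal event.
- In a PT row, it is confined to the fatal PT.

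**Step 2. Formula.** For an arm, let p be the proportion with worst grade ≥3 and f the proportion with worst grade 5.

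- Grade 3–4 column = p − f.
- Displayed difference between arms = (difference in p) − (difference in f).
- The sign reverses only if the arm with more Grade ≥3 participants has an excess in fatal TEAEs larger than its excess in Grade ≥3.

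**Step 3. Size in one arm.** Neither p nor f is in the documents; all values here are assumptions. The relative shortfall is f/p.

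| Assumed f | Column if p = 70% | Shortfall | Column if p = 50% | Shortfall |
|---|---|---|---|---|
| 2% | 68% | 3% | 48% | 4% |
| 5% | 65% | 7% | 45% | 10% |
| 10% | 60% | 14% | 40% | 20% |
| 15% | 55% | 21% | 35% | 30% |

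**Step 4. Comparison between arms (assumed rates).**

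- Reversal: Grade ≥3 of 70% vs 66%, fatal 10% vs 4%. True difference 4 points; fatal difference 6 points. The columns show 60% vs 62%, a difference of 4 − 6 = −2 points.
- No reversal: Grade ≥3 of 85% vs 75%, fatal 8% vs 4%. True difference 10 points; fatal difference 4 points. The columns show 77% vs 71%, a difference of 10 − 4 = 6 points.

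**Step 5. Weight of one participant.** The total randomized is redacted. Protocol 9.4.2 gives 190 for the CR analysis. At 2:1 that is 190 × 2/3 ≈ 127 and 190 − 127 = 63. If all are dosed, one participant with a fatal TEAE lowers the any-TEAE Grade 3–4 figure by 1/127 = 0.79 points in the tamibarotene arm or 1/63 = 1.59 points in the placebo arm.

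**Step 6. Missing-grade rule.** A fatal event with no recorded grade, and no earlier grade under that PT, becomes Grade 4 and is counted in Grade 3–4. The same event recorded as Grade 5 is not. More complete data give a lower severe-grade count.

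**The case against.** The strongest reply is that nothing is hidden.

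- Fatal TEAEs are in Any Grade, in the overall summary line and in the listings. The part of the deaths table within 30 days of the last dose covers about the same window as the TEAE definition.
- An event that results in death is serious by definition (Protocol 10.3.2), so it also enters the SAE tables by SOC and PT.
- Because missing grades are filled in, the Grade 5 count in a row can be recovered as Any Grade minus Grade 1–2 minus Grade 3–4.
- Deaths from disease progression are not adverse events (Protocol 8.3.6.1 and 10.3.1), which reduces the number affected.
- The tables are descriptive, with no test or stopping rule attached, and a column labelled Grade 3–4 does report what its label says. The sentence on grouping does not say that no other column may be shown, and SAP Section 4 lets minor template changes go undocumented in the CSR.

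All of this stands, and it limits the point to the by-grade tables. A reader might infer that severe toxicity is understated in the safety report as a whole; the outputs above show that it is not.

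What remains is a display rule that leaves Grade 5 without a column and gives no reason for doing so. The other outputs do not replace one. The deaths table includes progression deaths and is organized by cause, not by TEAE preferred term. The SAE tables do not separate fatal from non-fatal events. By-PT tables are planned for TEAEs leading to interruption, reduction and discontinuation, but not for those leading to death. Readers should not have to subtract columns to find fatal toxicity.

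**Conclusion.** The point holds for the by-grade TEAE tables. As written, they give neither a Grade ≥3 count nor a Grade 5 count, and the Grade 3–4 column falls below the Grade ≥3 rate by exactly the fatal-TEAE rate in that row. The effect is largest in the any-TEAE row.

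A reader might also infer that the arm with more fatal TEAEs will always show fewer participants in Grade 3–4. The documents do not support that: it depends on how the excess in fatal TEAEs compares with the excess in Grade ≥3, and the second example in the working goes the other way. What is certain is that the displayed difference departs from the Grade ≥3 difference by the difference in fatal TEAEs.

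The size cannot be computed from the documents, because they give no Grade ≥3 or fatal-TEAE rates. The conclusion rests on reading the grouping sentence literally, since the table shells are not available. This is a low-priority point about presentation, worth making because the correction is nearly free.

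**What to change.** In SAP 7.6.1 and the table shells:

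1. Add a Grade 5 column and a Grade ≥3 (3–5) column to every by-grade TEAE table, including those for related and selected TEAEs, and keep the existing columns.
2. Add a table of TEAEs leading to death by preferred term, alongside the planned tables for interruption, reduction and discontinuation.
3. State in SAP 7.6.1 and 7.1.3.9 that an adverse event with a fatal outcome and a missing grade is classified as Grade 5, ahead of the general missing-grade rule.

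The cost is SAP wording, shells and some programming. Data collection, sample size, alpha and patient management are unaffected.
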